8.5.1.4 Reporting Timelines

All reportable AEs and SAEs should be reported from the date of informed consent up to 7 days after each study procedure.

All unresolved adverse events should be followed by the investigator until one of the end of trial criteria is met (i.e. lost to follow up, withdrawal etc.). At the last scheduled visit, the investigator should instruct each participant to report any subsequent event(s) that the participant, or the participant’s general practitioner, believes might reasonably be related to participation in this trial. The investigator should notify the trial sponsor of any death or adverse event occurring at any time after a participant has discontinued or terminated trial participation that may reasonably be related to this trial.

8.5.2 Pre-existing Conditions

Pre-existing conditions (prior to informed consent) should not be reported as an AE unless the conditions worsen during the trial. The condition, however, must be reported on the selected pre-existing conditions of interest eCRF or clearly documented in the patient’s medical record.

8.5.3 Pregnancy

Given the deemed low risk of the intervention on pregnancy, pregnancy data will not be collected in the trial. If a patient becomes pregnant whilst participating in the trial, they become ineligible to remain in the trial and will be followed up as per standard care.

8.6 RESPONSIBILITIES

8.6.1 Principal Investigator (PI)

The PI, or medically qualified doctor who is registered on the delegation of responsibility log, is responsible for:

1. Using medical judgement in assigning seriousness, causality and if requested, whether the event/reaction was anticipated using the Reference Safety Information approved for the trial.
2. Ensuring that all SAEs and reportable device deficiencies are recorded and reported to the SCTU immediately, or at a least within 72 hours, of becoming aware of the event and provide further follow-up information as soon as available. Ensuring that SAEs are followed up with the SCTU if a record of receipt is not received within 1 working day of initial reporting.

3. Ensuring that all AEs are recorded and that ADEs are reported to the SCTU in line with the requirements of the CPSP.

8.6.2 Chief Investigator (CI) / delegate or independent clinical reviewer:

The CI, or delegated clinical reviewer, is responsible for:

1. Clinical oversight of the safety of patients participating in the trial, including an ongoing review of the risk / benefit.
2. Using medical judgement in assigning the event's seriousness, causality and whether if requested, the event was anticipated (in line with the Reference Safety Information) where it has not been possible to obtain local medical assessment.
3. Using medical judgement in assigning whether an event was anticipated and if requested, assessing expectedness in line with the Reference Safety Information.
4. Immediate review of all USADEs.
5. Review of specific events in accordance with the trial risk assessment and CPSP as required.
6. Upon request review Medical Dictionary for Regulatory Activities (MedDRA) or Body System coding to all events.

8.6.3 Sponsor / delegate

The Sponsor, or delegate, is responsible for:

1. Central data collection and verification of device deficiencies, AEs, and SAEs and USADEs according to the CPSP onto a database.
2. Reporting safety information to the CI, delegate or independent clinical reviewer for the ongoing assessment of the risk / benefit of the trial.
3. Checking causally related events against the approved RSI, in place at time of event onset.
4. Reporting safety information to the independent oversight committees identified for the trial
5. Sharing of all reported serious adverse events and device deficiencies with the manufacturer (or UK Responsible Person). SCTU will report these to MHRA on behalf of the manufacturer.
6. Ensuring that the expedited reporting of SAEs and reportable device deficiencies to the Competent Authority (MHRA in the UK) via MORE portal, are within the required timelines.
7. Ensuring expedited reporting of related and unexpected serious adverse events to the REC within the required timelines.

8. Authoring and submission of Quarterly Summary Reports to the Competent Authority (MHRA in the UK) via MORE portal, within the required timelines.
9. Notifying Investigators of related and unexpected serious adverse events that occur within the trial.
10. Notifying PIs of updates to the Reference Safety Information for the trial.

8.6.4 WISH Laboratory and ClearNote Health laboratory

Each laboratory is responsible for:

1. Recording any device deficiencies occurring at their respective laboratories onto a CRF and sharing these with SCTU on an ad-hoc basis (at least quarterly) as requested for onward reporting to MHRA within the required timelines.

8.7 REPORTING URGENT SAFETY MEASURES

If any urgent safety measures are taken the CI/Sponsor shall immediately, and in any event no later than 3 days from the date the measures are taken, give written notice to the MHRA and REC of the measures taken and the circumstances giving rise to those measures.

8.8 QUARTERLY SAFETY REPORTS (QSR)

SCTU (on behalf of the manufacturer) will provide quarterly summary reports to the MHRA via the MORE portal, following internal standard operating procedures as well as the latest MHRA guidance. The first report is to be submitted as soon as possible after the end of the first quarter after the first patient sample has been tested. In this study, “first treatment” will be the day that the first patient has their first visit.

9 STATISTICS AND DATA ANALYSES

9.1 METHOD OF RANDOMISATION

Participants will be randomised to the control or intervention arm (1:1 ratio) via an independent, web-based system (www.imedidata.com) by a delegated member of the WISH laboratory team. The randomisation list will be pre-generated with permuted blocks of differing lengths. Participants will remain blinded until planned unblinding occurs (see section 7.5.2).

9.2 SAMPLE SIZE

Upon conclusion of the pilot, further recruitment to the study will occur with a planned interim analysis for futility and efficacy. Participants in the pilot study will continue to have their data analysed. The planned interim analysis is referred to as ‘stage 1’ analysis for convenience. The final analysis is referred to as ‘stage 2’ analysis. In each stage, there are three co-primary endpoints:

1. sensitivity (of the Avantect test),
2. specificity (of the Avantect test) and

3. resectability of diagnosed PCs

In the stage 1 interim analysis, these endpoints will be assessed within the intervention arm, as more information will be available on the diagnostic status of this group. In the stage 2 final analysis, the sensitivity and specificity of the test will be estimated within the intervention arm, whereas resectability will be compared between the arms.

The anticipated prevalence of a pancreatic cancer diagnosis within 3-years of follow-up within this population is 1%³. Conservative estimates place the anticipated sensitivity of the Avantect test at 65% sensitivity and 95% specificity in the detection of PC. Under usual care in the UK, 10-20%^{13,14} of pancreatic cancer patients receive surgery with curative intent due to the majority (80%) presenting at Stage III or Stage IV¹⁵. Data from the CAPS cohort¹⁶ in the US has demonstrated that it is possible to reduce the proportion of patients presenting with late stage disease if surveillance testing is conducted on at-risk subgroups, thus improving the availability of curative resection as a treatment strategy. It is hoped that the Avantect test can improve the resectability of pancreatic cancers from a rate of 14% in usual care to 40% in the intervention arm (just over a 2.5-fold increase).

With three co-primary endpoints, each endpoint must be reached for an overall successful result. To achieve an overall power of 90%, the power for each endpoint should be $90\%^{(1/3)} = 96.5\%$. Following guidance from Korevaar and colleagues¹⁷, the analysis will consist of a one-sided test at an cumulative alpha of 0.05 at the final analysis. Because there is an interim analysis at stage 1 for efficacy and futility, the one-sided significance level changes at the interim and final analysis.

Two of the three co-primaries are metrics of test accuracy. In practice test results will not be available for all participants due to machine failure, insufficient blood sample quality, shipping or processing, or participants being unable to provide a blood sample. To reduce the number of participants where no test results are available, three collection time points are included. In the case where a blood draw did not occur or the sample was not analysable following a scheduled visit, a repeat blood draw will be arranged. The expected proportion of participants who are expected to not have a single Avantect result is 2.5%.

Using the PropTestPower function in the R package EnvStats, it was determined that 73 individuals with pancreatic cancer are required in each arm to detect a change of resectability from 14% in usual care to 40% in the intervention arm. At the stage 2 final analysis, allowing for interim analysis, the overall power would be 96.5%. Allowing for 2.5% loss to arrive at the Per Protocol population (see section 9.4), this increases to 75 cases per arm (150 total), which at an event rate of 1% leads to a recruitment target of 7,500 per arm (15,000 total). As only samples from the intervention arm are to

be tested for the purpose of the analysis, with an anticipated test sensitivity of 65% and specificity of 95%, this leads to the following confusion matrix in the intervention per protocol group (7,312):

		Diagnostic status	
		Has PC diagnosis	Does not have PC diagnosis
Avantect test result	Detected	48	362
	Not detected	25	6,877

With 73 cases of pancreatic cancer of which $48/73 = 65\%$ were detected by the Avantect test, this would be sufficient to rule out a sensitivity lower than 42 % in the stage 2 final analysis at 96.5% power. On discussion with the FDA, a specificity of 92% would be considered acceptable within this clinical context. With 6,877 individuals without a pancreatic cancer diagnosis of which $6,877/7,239 = 95\%$ are expected to be detected by the Avantect test, more than 99% power is achieved to rule out a specificity lower than 92%.

Definition of ‘promising result’ in study stage 1 to guide progression to study stage 2

An analysis for futility and efficacy will be conducted once 3,200 individuals randomised to the intervention arm have returned for the third blood-draw (T2) in order to obtain cancer outcome data from the cancer registry. This amounts to 43.8 % of the total information accrual in the intervention arm, accounting for 2.5% not qualifying for the Per Protocol population (see 9.4; $3,200/7,312$). All individuals with one or more Avantect “detected” test results will be included as positive predictions. Individuals whose Avantect test results are all “not detected” will be included as negative predictions. Based on a cumulative one-sided alpha of 0.05 and 96.5% power for the three co-primary outcomes, the futility and efficacy thresholds at stage 1 interim analysis are detailed in the table below. If all study endpoints are deemed futile, or in the scenario that all study endpoints are deemed efficacious the study will stop at this stage. If all of the study endpoints are deemed promising then the study will continue to stage 2. If there is a combination of results, the Trial Steering Committee (TSC) and IDMC will decide whether the study progresses to stage 2.

	Expected proportion	Futility threshold at stage 1	Promising result range at stage 1	Efficacy threshold at stage 1
Sensitivity	65%	<46.5%	46.5% to 63.1%	>63.1%
Specificity	95%	<92.0%	92.0% to 94.9%	>94.9%
Resectability	40%	<21.0%	21.0% to 38.1%	>38.1%

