2. CLINICAL PERFORMANCE STUDY OBJECTIVES AND ENDPOINTS

2.1 PRIMARY STUDY OBJECTIVES

The study will be divided into a pilot and two stages:

- Pilot: The goal of the six-month pilot is to determine if the enrolment strategy (identifying eligible subjects via commercial recruitment platforms, NIHR Research Delivery Network Primary Care Networks and Specialist Diabetes Service Centres (SDSC)) is adequate, and to identify barriers and develop mitigation strategies to improve recruitment. Participants may also self-refer to the study following viewing study information found on the study website or displayed in Primary Care locations. The pilot will also assess the BMI distribution to determine whether body mass index (BMI) should be included as eligibility criteria in study stage 1 and 2. We will aim to open up to 450 Participant Identification Centres (PICs) during the pilot and at least 30 recruitment hubs where participants can attend for study visits (also referred to as sites).
- The pilot will be considered successful if:
 - Recruitment rate is greater than 10% of invitation to enrolment, or
 - 800 participants are enrolled, or
 - Enrolment is greater than an average of 133 participants per month in the last three months of pilot
- The feasibility of continuation to study stage 1 and 2 will be assessed by the Trial Steering Committee based on recruitment during the pilot
- Study stage 1 will enrol an additional 5,600 NOD participants with the primary objective to evaluate sensitivity and specificity of the Avantect test in detecting pancreatic cancer in 3,200 intervention arm participants with 1 year of follow-up for futility and efficacy.
- Study stage 2 will enrol an additional 8,600 participants to make a total of 15,000 NOD participants with the primary objectives of evaluating sensitivity and specificity of the Avantect test in detecting pancreatic cancer in intervention arm participants, and comparing the proportion of pancreatic cancers deemed resectable across the intervention and control arms.

2.2 PRIMARY ENDPOINTS:

- Pilot: Recruitment rate - number of NOD individuals enrolled into the study divided by the number of individuals invited to participate.
 - Recruitment rate to be greater than 10% of invitation to enrolment OR
 - 800 participants are enrolled OR
 - Enrolment is greater than an average of 133 patients per month in the last 3 months of the pilot.
- Study stage 1 and 2:

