2.4 TABLE OF ENDPOINTS/OUTCOMES PILOT

	Objective	Outcome Measures	Summary method(s)
Primary	To determine the recruitment rate	Recruitment rate	
 Percentage recruited of all participants invited Number of individuals recruited per month

STUDY STAGE 1 and 2 (analysis inclusive of pilot):

	Objective	Outcome Measures	Summary method(s)
Primary	To estimate the proportion of PCs deemed resectable	Resectability rate	Percentage of PCs deemed resectable by the study MDT [compared between arms]
	To estimate the sensitivity of the Avantect test in detecting PC	Sensitivity	Percentage with PC diagnosed who have an Avantect “detected” result [within intervention arm]
	To estimate the specificity of the Avantect test in ruling out PC	Specificity	Percentage without PC diagnosed who have one or more Avantect “not detected” results and no Avantect “detected” results [within intervention arm]
Secondary	To determine the effect of the Avantect test on PC stage shift	Stage shift	Percentage of PCs diagnosed at stage I/II [compared between arms]
	To estimate the PPV of Avantect for detecting PC	PPV	Percentage with an Avantect “detected” result who have PC diagnosed [within intervention arm]

	To estimate the NPV of Avantect for ruling out PC	NPV	Percentage of individuals with no Avantect “detected” test results who have no diagnosis of PC [within intervention arm]
	To estimate the proportion of PCs that are resected	Resection	Percentage with PC who underwent resection [compared between arms]
Exploratory	To estimate the time from NOD diagnosis to PC diagnosis	Time to diagnosis	Kaplan-Meier curve Hazard ratio [within intervention arm]
	To estimate the overall survival of study participants	Overall Survival	Kaplan-Meier curve Hazard ratio [compared between arms]
	Assess the effect of the Avantect test on state anxiety over time	6-item STAI	T-test or non-parametric alternative if suitable [compared between arms]
	To investigate the performance characteristics for high-grade neoplasia	Sensitivity Specificity PPV NPV	As described above, but disease positive is defined as PC and/or high-grade mucinous cysts and non-cases defined as no pancreatic cancer or high-grade mucinous cysts. This will be repeated where high-grade mucinous cysts are considered as disease positive and PCs are excluded. [within intervention arm]

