5. SELECTION AND ENROLMENT OF PARTICIPANTS

5.1 PARTICIPANT ENROLMENT

Participants will be approached to take part in SAFE-D via their GP or SDSC. Electronic Health Record (EHR) searches will be undertaken by the study team at participating GP practices and subjects with a recent diagnosis of DM (within six months) will be eligible for enrolment. Subjects attending SDSCs will also be eligible for enrolment. In addition, participants may self-refer for the study via the SAFE-D booking website. Participants who sign the consent form will be considered enrolled.

The study is expected to enrol 15,000 participants over 36 months, including a six-month pilot study to evaluate recruitment feasibility and to estimate the number of participating sites required, and an interim analysis for futility and efficacy (Stage 1). Participants will remain in the study for 12 months, attending study visits at enrolment (baseline (T0)) and at six (T1) and 12 months (T2) post enrolment. There may be planned recruitment stops between the Pilot and Stage 1 of the study to allow for a data driven 'stop-go' decision should this decision not be concluded in the lead up to Stage 1. Recruitment will continue once the Stage 1 interim analysis requirements have been met and will continue unless that analysis concludes that the intervention is futile. Total study duration is expected to be 7 years including 12 months for analysis and report writing.

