10.3 AMENDMENTS/MODIFICATIONS

The CPSP, PIS, informed consent form (ICF) and other subject information or other study documents (e.g. Instructions for Use) shall be amended as needed throughout the study in accordance with local SCTU written procedures for the control of documents and document changes. Proposed amendments to the CPSP will be reviewed and authorised locally in accordance with SCTU procedures. Any amendments to the CPSP, PIS and ICF shall be notified to the REC and will only be implemented once clinical performance study authorisation has been received.

Local SCTU procedures will be followed in the event that the clinical performance study requires either a temporary halt, or early termination. In the event of early termination of the clinical performance study, there will be no requirement for additional follow-up or continued care for study participants.

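### Stage 1 can stop the randomised trial for success on intervention-arm data alone, with an assumed 14% standing in for the control arm's resectability rate

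*Protocol*

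**What the plan says.** Section 9.2 of the protocol sets three co-primary endpoints. For Stage 1 it states: "In the stage 1 interim analysis, these endpoints will be assessed within the intervention arm". The reason given is that diagnostic status will be better known in that arm. At Stage 2, sensitivity and specificity stay within the intervention arm, "whereas resectability will be compared between the arms".

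The tables in 9.2 and 9.4 class Stage 1 resectability as futile below 21.0%, promising from 21.0% to 38.1%, and efficacious above 38.1%. Section 9.4 adds a one-sided 98.6% lower bound on the observed proportion. The stopping rule in 9.2 is that "in the scenario that all study endpoints are deemed efficacious the study will stop at this stage". The study also stops if all endpoints are futile. Otherwise: "If there is a combination of results, the Trial Steering Committee (TSC) and IDMC will decide whether the study progresses to stage 2".

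Other sections read differently:

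- Section 2.1 names only sensitivity and specificity as the Stage 1 objective. Among the Stage 2 primary objectives it places "comparing the proportion of pancreatic cancers deemed resectable across the intervention and control arms".
- Section 2.4 labels resectability as compared between arms, under a heading that covers both stages.
- Section 5.1 says of recruitment after the interim that it "will continue unless that analysis concludes that the intervention is futile". This leaves no room for an efficacy stop.

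**The concern.** Resectability is the only co-primary that needs the control arm. At Stage 1 it is judged as a single proportion against a fixed cut-off. If it crosses together with sensitivity and specificity, the trial stops for success and no randomised comparison of resectability has been made.

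The validity of that decision then rests on an assumed usual-care rate of 14%. Section 9.2 supports it with the share of patients who receive potentially curative surgery (10-20%). The endpoint is a different quantity: cancers judged resectable by the study team, whether or not surgery follows. The protocol's figures on early-stage disease also do not settle the rate. Section 9.2 cites 80% presenting at stage III or IV in usual care, while section 9.4 expects 35% of control-arm cancers at stage I/II. Stage I/II is not the same as resectable, but the spread shows that the control rate is uncertain. A concurrent control arm would resolve that.

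**Working it through.** **Inputs.** 3,200 intervention participants at Stage 1; 1% prevalence; 2.5% without a usable result; rates of 14% and 40%; Stage 1 cut-offs of 38.1%, 63.1% and 94.9% (all section 9.2). One-sided 98.6% interval, so alpha 0.014 (section 9.4).

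**Expected cancers.** The protocol does not state the Stage 1 number. Section 9.2 computes the information fraction as 3,200/7,312 = 43.8%, which treats 3,200 as per-protocol: 3,200 x 0.01 = 32. Taking the 2.5% off first gives 3,200 x 0.975 x 0.01 = 31.2, or 31. Both counts are carried below.

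**Reproducing 38.1%.** Use the pooled two-sample test with 32 per arm and control fixed at 14%:

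z = (p - 0.14) / sqrt[pbar(1 - pbar) x 2/32], with pbar = (p + 0.14)/2.

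At p = 0.381, pbar = 0.2605, the standard error is 0.1097 and z = 0.241/0.1097 = 2.20. The critical value for alpha 0.014 is 2.197; solving exactly gives p = 38.1%. A one-sample test against 14% would give 0.14 + 2.197 x sqrt(0.14 x 0.86/32) = 27.5%. So the tabulated cut-off is a two-arm critical value with an assumed constant in place of the observed control rate.

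**Chance that resectability crosses with no test effect.** Exceeding 38.1% needs 12 of 31 or 13 of 32. Exact binomial P(X >= r | n, p):

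| True resectable rate | 31 cancers | 32 cancers |
|---|---|---|
| 14% | 0.0006 | 0.0002 |
| 20% | 0.013 | 0.006 |
| 25% (assumed) | 0.064 | 0.038 |
| 30% (assumed) | 0.19 | 0.13 |
| 35% (assumed) | 0.40 | 0.31 |

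**Chance that all three cross.** At sensitivity 65%, P(above 63.1%) is 0.603 with 31 cancers (20 needed) and 0.551 with 32 (21 needed). At specificity 95%, P(above 94.9%) is 0.604 for either count. Treating the endpoints as independent:

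- 31 cancers: 0.603 x 0.604 = 0.364. Multiplied by 0.064, 0.192 and 0.397, this gives 2.3%, 7.0% and 14%.
- 32 cancers: 0.551 x 0.604 = 0.333. Multiplied by 0.038, 0.133 and 0.310, this gives 1.3%, 4.4% and 10%.

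**What the control arm would add.** With 13/32 in the intervention arm, which the rule always calls efficacious, the one-sided between-arm p-value depends on the controls: 0.005 at 4/32, 0.013 at 5/32, 0.028 at 6/32, 0.092 at 8/32 and 0.217 at 10/32. The 0.014 level is met only if the observed control rate is about 16% or lower.

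**Fewer cases.** The 1% is a 3-year figure and Stage 1 follow-up is about 12 months, so fewer cancers are likely. As an assumption, with 16 cancers (7 needed) the crossing chance is 0.027 at a 20% rate and 0.080 at 25%. With 10 cancers (4 needed) it is 0.12 and 0.22.

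**Futility rule.** With true specificity 95% and about 3,089 non-cases, P(observed specificity below 92%) is about 6e-13. The all-futile condition then practically cannot be met, whatever sensitivity and resectability show.

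**The case against.** The strongest defence is that the bound is sound under the protocol's own assumptions. Usual-care resectability is taken as 14% and surgery as 10-20%. Over that range, with 31 or 32 cancers, the crossing chance is at most about 1.3%, inside the 1.4% allotted. The 38.1% cut-off is also much stricter than the 27.5% of a one-sample test. This stands: the documents do not show an inflated error rate. The 25-35% rates are assumptions, not protocol figures.

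Second, resectability alone does not trigger the automatic stop, so a reader who took 31-40% as the chance of a false stop would overstate it. The joint figures apply, and if sensitivity were at 42%, the rate section 9.2 sets out to rule out, they fall below 0.3%. Mixed results go to the TSC and IDMC. This also stands.

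Third, a reader might infer that the randomised question would be lost for good. Section 10.3 says that after early termination "there will be no requirement for additional follow-up or continued care for study participants", but it does not forbid follow-up, and controls would already be randomised. The protocol simply specifies no between-arm analysis for that case.

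Fourth, a reader might call the futility rule inverted, since every co-primary must succeed but all must be futile for an automatic stop. That goes too far, because a single futile endpoint already reaches the TSC and IDMC.

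The stated reason for using one arm, better diagnostic information there, explains the choice. It does not supply the missing comparison.

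**Conclusion.** The concern holds in a limited form. Stage 1 can end the trial for success with no use of the control arm, although resectability is a between-arm primary endpoint, and section 5.1 contradicts section 9.2 on whether efficacy stops recruitment at all. The error rate of the resectability decision depends on an assumed 14% drawn from a surgery rate. It is acceptable if the true usual-care rate is 14-20% and about 31-32 cancers accrue. Under assumed no-effect rates of 25%, 30% and 35%, resectability crosses with probability about 4-6%, 13-19% and 31-40%, and all three endpoints with about 1-2%, 4-7% and 10-14%. The joint figures take sensitivity as 65%, specificity as 95%, and independence. The case for change rests on the unused control arm and the conflicting sections, not on demonstrated error inflation.

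A secondary point is that the automatic futility stop is practically inert if specificity is 95%. Committee review of mixed results limits the consequence.

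**What to change.** Either remove the Stage 1 efficacy bound for resectability, so that the endpoint is futility-only at the interim, or allow an efficacy stop only after a between-arm test of resectability.

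The second option needs study-team imaging review in both arms by Stage 1. The registry download planned at 6,400 recruited covers both arms, but the fields listed in section 7.6.4 include no resectability assessment, so registry data alone cannot supply the endpoint. With about 32 cancers per arm, 14% against 40% and one-sided alpha 0.014, that test would have about 56% power.

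Then reconcile sections 2.1, 2.4, 5.1, 9.2 and 9.4 on which endpoints Stage 1 tests, in which arms, and whether an efficacy finding stops the study. In the same edit, say whether the all-futile condition is meant to act as a working stop or whether futility is in practice left to the TSC and IDMC.

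The first option costs only protocol wording; the second also needs control-arm scans collected and reviewed earlier. With either, an early efficacy stop becomes less likely. Under the design assumptions with 32 cancers, the present rule would give one about 18% of the time (0.54 x 0.55 x 0.60, independence assumed).
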